### Safety

- Frequency and severity of adverse events and unanticipated adverse device effects (UADEs)
- Evaluation of clinical and laboratory findings
- · Concomitant medication assessment
- Frequency and severity of gastrointestinal signs and symptoms (abdominal pain, vomiting, loss of appetite, bloating, flatulence and steatorrhea)

### 4.0 STUDY DESIGN AND PROCEDURES

### 4.1 Enrollment Goals

Male and female patients with CF and EPI will be screened for the study from approximately 10 investigative centers in the United States. Approximately 35 subjects will be enrolled in the study with the goal of having at least 30 evaluable subjects completing the study through at least Visit 4 (Day 60).

# 4.1.1 Representative Age Groups

This study will enroll patients with CF who are 4 years of age or older without an upper age limit. Since median predicted survival age for patients with CF is approximately 40 years, it is expected that the majority of patients enrolled will be less than 40 years old.

To obtain a diverse age range in the study population, the PIs will be encouraged to recruit patients along the age continuum. Since study sites are pediatric centers, it is expected that the majority of subjects will be in the pediatric age range. However, PIs at study sites will be encouraged to collaborate with affiliated adult CF centers to allow for the recruitment of adult patients with CF.

Subjects discontinuing study participation may need to be replaced to achieve the minimum total number of 30. All available data for subjects who were enrolled and discontinued will be captured in data reports. Patients who participated in Protocol 0000497 and considered to be protocol compliant will be eligible for enrollment in

Title: Absorption and Safety with Sustained Use of Relizorb™ Evaluation (Assure) Study in Patients With Cystic Fibrosis Receiving Enteral Feeding

Protocol 0000498. In addition, Relizorb naïve patients that meet eligibility criteria may enroll. It is anticipated that active enrollment will last approximately three and a half months.

# 4.2 Study Duration

The anticipated study duration is approximately 104 days. This includes a 7 day observation period when the subject is maintaining their usual care routine, a 7 day run in period, and a 90 day open label treatment period. Subjects who experience a UADE during the last 29 days of the open label period will be followed for 30 days following the occurrence of the UADE or until resolution, whichever comes first.

# 4.3 Study Periods

The study will have three periods: a 7 day observation period that will establish a baseline, a 7 day run in period that will normalize the enteral formula type and volume of the feeding, and a 90 day treatment period. Study visits and the attendant tests and procedures should be performed according to schedule. However, changes in scheduled study visits are allowed with permission from the site for holidays, vacations, etc. For these exceptions, the study visit should occur within 4 days (4) of the scheduled day. There will be five study visits as described below:

# Visit 1: Study Entry (Day -14)

On Visit 1 (Day -14), subjects (or legally authorized parent or guardian) will sign a written informed consent, or assent when applicable. Baseline procedures will include evaluation of eligibility criteria and recording or obtaining demographics, medical history, physical examination, height, weight, body mass index, vital signs, standard clinical laboratory tests (hematology, clinical chemistry, urinalysis), blood lipids, urine sample for urinary leukotriene evaluation, plasma fatty acid sample, pregnancy test for childbearing females and concomitant medications. Collected results on Day -14 will be used to screen patients for eligibility and characterize the study population. Study staff will also review the medical records and obtain up to four body weight measurements recorded at 3 month intervals over the previous 12 months. Historical average daily PERT use with meals and snacks and with enteral nutrition will be recorded. Study staff will provide detailed instructions for subjects to maintain a gastrointestinal symptom diary for 7 consecutive days.

During the observation period (Day -14 to Day -8), subjects will maintain their usual care plan. The brand, volume, and administration rate of the enteral formula used in the enteral feeding will be recorded, along with the usual dose of PERT use associated with the enteral feeding. Crushing of PERT products and adding to the enteral feeding bag is prohibited. Subjects will make entries into a 7-day gastrointestinal symptom

Title: Absorption and Safety with Sustained Use of Relizorb™ Evaluation (Assure) Study in Patients With Cystic Fibrosis Receiving Enteral Feeding

diary each day. PERT use with meals and snacks and with enteral tube feeding will be recorded each day by the subject.

During the run in period (Day -7 to Day -1), subjects will maintain their usual enteral feeding volume up to a maximum volume of 1000 mL and administration rate using Peptamen 1.5 for at least 5 days preceding the treatment period between Day -7 and Day -1. The usual dose of PERT use associated with the enteral feeding will be allowed, but crushing of PERT products and adding to the enteral feeding bag is prohibited. Subjects will make entries into a 7-day gastrointestinal symptom diary each day. PERT use with meals and snacks and with enteral tube feeding will be recorded each day by the subject. Peptamen 1.5 for use during the run in period will be shipped to the subject's home prior to Day -7.

Visit 2: Baseline (Day 0)

During Visit 2, as well as each subsequent visit, the study staff will collect the completed gastrointestinal symptom diary. Blood samples will be collected for fatty acid, protein, and fat-soluble vitamin analysis during these visits. In addition, a urine sample will be collected for urinary leukotriene analysis. Body weight and height will be measured and recorded, and BMI will be calculated and recorded. Each subject and/or parent(s) will receive verbal instructions on the temperature storage, setup and operation of Relizorb with Impact Peptide 1.5. Study staff will physically demonstrate setup and operation of Relizorb so that subjects/parents receive hands-on training prior to leaving the clinic. Study staff will instruct subjects/parents/caregivers on recording the use of Relizorb between study visits. Subjects and parents will have the opportunity to ask questions to ensure familiarity with the principles of operation. This will ensure that subjects/parents are knowledgeable regarding the proper use of formula with either the Covidien Kangaroo™ ePump or MOOG Enteral Lite® Infinity® pumps. Instructions For Use (IFU) will be provided to subjects/parents to take home.

Impact Peptide 1.5 is the only enteral formula allowed for use for enteral tube feedings in this part of the study. Subjects will maintain their usual enteral feeding volume up to a maximum volume of 1000 mL and administration rate using Impact Peptide 1.5. Study staff will inform subjects/parents that any use of PERT in association with the enteral tube feeding is strictly prohibited.

On or before Day 0, all subjects will receive outpatient study supplies, such as the Relizorb investigational device, Impact Peptide 1.5, Relizorb Accountability Log, 7-day gastrointestinal diary and specific written instructions. Subjects/parents/caregivers will be informed that they should start a 7-day gastrointestinal diary one week before the next study visit so it is completed the day before the next study visit. Subjects will be instructed to maintain their normal CF treatment regimen and usual diet throughout the study. No dietary restrictions exist during the outpatient period. Subjects should follow

Title: Absorption and Safety with Sustained Use of Relizorb™ Evaluation (Assure) Study in Patients With Cystic Fibrosis Receiving Enteral Feeding

dietary recommendations from their registered dietitian (RD), nutritionist or healthcare professional.

# Visits 3, 4, and 5: Treatment Period (Days 30, 60, and 90)

Approximately one week before visits 3, 4, and 5, study staff will contact subjects/parents/caregivers and remind them to start a 7-day gastrointestinal diary such that it is completed the day before the study visit, and also remind them to bring the completed diary with them to the clinic visit along with all used and unused Relizorb cartridges. During these visits study staff will collect the completed 7-day gastrointestinal symptom diary. Blood samples will be collected for fatty acid, protein, and fat-soluble vitamin analysis during these visits. In addition, a urine sample will be collected for urinary leukotriene analysis. Body weight and height will be measured and recorded, and BMI will be calculated and recorded. Study staff will assess UADEs and concomitant procedures and medication use.

Study staff will review the Relizorb Accountability Log for completeness, collect all used Relizorb cartridges, and provide subjects with additional unused Relizorb cartridges for at home use until the next scheduled visit. Concomitant medications and UADEs will be assessed.

Subjects who experienced a new or ongoing UADE within the previous 29 days will receive a follow-up safety contact until 30 days after the occurrence of the UADE or until the UADE has resolved, whichever comes first. Therefore the duration of the study may be extended if a subject has a new or ongoing UADE between Day 60 and Day 90.

On the final clinic visit (Day 90), the majority of baseline procedures will be repeated. End of study procedures will include standard laboratory testing (clinical chemistry, hematology and urinalysis), blood lipids, vital signs, weight, and height measurement, and BMI calculation.

Subjects will be instructed to bring to the clinic all used and unused devices to enable study staff to check administration compliance. All used and unused cartridges will be inventoried and returned to the Sponsor, unless destruction at the study site is authorized.

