### STUDY SCHEMATIC

### Table 1: Schedule of Events

	Visit 1	Visit 2	Visit 3	Visit 4	Visit 5 *
Evaluation	Day -14 Study Entry	Day 0 Baseline	Day 30 Treatment	Day 60 Treatment	Day 90 End of Study
Informed Consent	X				
Inclusion / Exclusion Criteria	X				
Demographics	X				
Medical History a	X				
Physical Examination	X				X
Height, Weight, Body Mass Index b	X	X	X	X	Х
Vital Signs c	X	X	X	X	Х
Hematology d	X				X
Clinical Chemistry e	X				Х
Urinalysis f	Х				Х
Blood Lipids g	X	Х	X	Х	X
Serum Proteinsh	Х	Х	X	Х	Х
Serum Pregnancy Test (β-hCG) i	Х				
Urinary Leukotrienes	X	Х	X	Х	X
7-Day Gastrointestinal Symptom Diary	X	X	X	Х	X
Plasma Fatty Acid Samples j	X	X	X	Х	Х
Vitamins A, D, and E k	X	Х	X	Х	X
Peptamen® 1.5 500 to 1000 mL 	Х				
Impact® Peptide 500 to 1000 mL		Х	X	Х	X
Relizorb Administration		×			
Relizorb Accountability Log		X			
Unanticipated Adverse Device Effects		Х			

Note: Tests and procedures should be performed according to the above schedule but changes in scheduled study visits (±4 days) are allowed with permission from the site for holidays, vacations, etc. The amount of blood taken from subjects will be limited to no more than 3 mL/kg in 24 hours and no more than 7 mL/kg over the course of the study.

Title: Absorption and Safety with Sustained Use of Relizorb™ Evaluation (Assure) Study in Patients With Cystic Fibrosis Receiving Enteral Feeding

- \* If any Unanticipated Adverse Device Event (UADE) is reported on Day 90, then a safety follow-up telephone call will occur on Day 91, and the subject will be followed until either resolution of the event or for 30 days, whichever is shorter.
- a. A complete medical history will be obtained.
- b. Height and weight will be measured and recorded, and BMI will be calculated and recorded at each study visit. Four weight and BMI measurements recorded at 3 month intervals over the previous 12 months before Day -14 will be obtained from the medical record.
- c. Vital signs will include blood pressure, pulse rate, respiratory rate and oral/tympanic temperature and will be obtained on in-clinic days.
- d. Hematology includes complete blood count and white blood cell differential.

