### 6.2 Adverse Events

An adverse experience (AE) is defined as any untoward medical occurrence in a subject, regardless of its causal relationship to the investigational device. An AE can therefore be any unfavorable and unintended sign (including abnormal laboratory

Title: Absorption and Safety with Sustained Use of Relizorb™ Evaluation (Assure) Study in Patients With Cystic Fibrosis Receiving Enteral Feeding

findings), symptom or disease experienced with use of the product, whether or not it is related to the product. This includes any newly occurring event or a previous condition that has increased in severity or frequency since the use of Relizorb.

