## 7.7 Safety Analysis

Safety will be assessed based on the incidence, severity, and type of AE and UADE, clinically significant changes or abnormalities in the subject's clinical laboratory results and vital signs. For clinical laboratory tests, descriptive summaries of actual values and changes from the baseline will be presented. Descriptive statistics will be provided for vital sign measurements collected during clinic visits.

AE and UADEs will be recorded throughout the study and listed in summary tables in terms of severity and causal relationship to Relizorb use. Relationship assessments that indicate the AE is "Not Related" is an event related to etiology, rather than from Relizorb use. "Related" is defined as an association between the AE or UADE and Relizorb use. Other selections include "Possibly Related" and "Probably Related".

The gastrointestinal symptoms recorded in the 7 day gastrointestinal symptom diary during the run in period will be compared with the symptoms recorded three separate times during the treatment period. Each symptom will be categorized as a) occurring or not occurring b) rated as a 1,2, or 3 in severity, and lasting in duration for less than 15 minutes, 15 to 30 minutes, 31 to 60 minutes, or greater than 60 minutes.

For the comparison between symptoms recorded during the run in period and the treatment period, the following analyses will be performed:

Number of days where any symptom occurred;

Title: Absorption and Safety with Sustained Use of Relizorb™ Evaluation (Assure) Study in Patients With Cystic Fibrosis Receiving Enteral Feeding

- Number of days each symptom occurred;
- For each symptom, number of days when the severity was a 1, 2, and 3
- For each symptom, number of days when the symptoms lasted in duration for less than 15 minutes, 15 to 30 minutes, 31 to 60 minutes, or greater than 60 minutes.

Comparison of these values during the run in and treatment periods will be performed using analysis of variance (ANOVA).

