9.1 Adverse Events

All AEs will be coded using the Medical Dictionary for Regulatory Activities (MedDRA Version 18.0 or most recent version).

AEs will be summarized by MedDRA system organ class and preferred term. Separate columns will be included in the AE summary table for AEs starting under the treatment by Standard of Care, and starting during RELiZORB treatment.

For all AEs, the event will be summarized under the treatment (Standard of Care, RELiZORB) the event started in and in the total column. The AE is assigned to the standard of care or RELiZORB based on the start date of the adverse event.

- If the start date of the event is before the first administration of RELiZORB, the event will be summarized under Standard of Care.
- If the start date of the event is on or after the first administration of RELiZORB, the event will be summarized under RELiZORB.
- If the start and end date of the event are both missing, the event will be summarized under both SOC and RELiZORB.

In a general overview of AEs, events will be summarized by treatment for the following items:

- All AEs
- Serious Adverse Events (SAEs)
- AEs by relationship
- AEs leading to discontinuation of enteral feeding
- AEs by maximum severity
- UADEs
- UADEs by relationship
- UADEs leading to discontinuation of enteral feeding
- UADEs by maximum severity

Missing and partially missing AE start and/or stop dates will be imputed, for the purpose of statistical analysis, according to the specifications described in Section 6.2.

Summaries of incidence rates (frequencies and percentages) of individual AEs by MedDRA System Organ Class and preferred term will be prepared. UADEs and SAEs will not be included in summaries of AEs, but will be summarized separately. Each subject will be counted only once within each level of summary (system organ class and preferred term).

Adverse events that lead to discontinuation of enteral feeding will be summarized and listed separately.

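### The documents conflict on AE collection: the analysis tabulates non-serious AEs before and after the device, but the schedule and visit text name UADEs only and no start of AE collection is stated

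*Protocol*

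**What the plan says.** **Passages that call for AEs.** The protocol synopsis says AEs and UADEs are recorded, and 7.7 states "AE and UADEs will be recorded throughout the study". How often AEs occur and how severe they are heads the safety endpoints in both documents. SAP 9.1 allots each AE to a column by its start date: "If the start date of the event is before the first administration of RELiZORB, the event will be summarized under Standard of Care". Events that start on or after first use go in the RELiZORB column. The summaries of individual AEs by system organ class and preferred term leave out UADEs and SAEs.

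**Passages that tell sites what to do at a visit.** Table 1 (protocol and SAP) has one row for safety events, "Unanticipated Adverse Device Effects", and none for AEs. The Visit 1 procedures end with "pregnancy test for childbearing females and concomitant medications" and do not mention AEs. The Visit 2 text does not mention them either. The text for Visits 3 to 5 says "Study staff will assess UADEs and concomitant procedures and medication use" and then repeats "Concomitant medications and UADEs will be assessed".

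**The definition (protocol 6.2).** It opens with "any untoward medical occurrence in a subject, regardless of its causal relationship to the investigational device". The second sentence then speaks of findings that arise while the product is used, and the third reads "This includes any newly occurring event or a previous condition that has increased in severity or frequency since the use of Relizorb".

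**The concern.** The AE tables depend on a category of event that the visit instructions do not name. This matters most before the device. The Standard of Care column is the only AE comparator within this single-arm study, and it covers a period for which no AE enquiry is scheduled and for which part of the AE definition seems not to apply. If sites read the instructions differently, the column will reflect site practice as well as what happened to subjects. About 10 sites are planned, so practice may well vary. During treatment, an enquiry limited to UADEs would miss non-serious events, which are most of what tolerability consists of. Missing events of either kind cannot be recovered at analysis, and incomplete capture cannot then be told apart from a device effect.

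**Working it through.** The documents give no AE rate and no capture fraction, so there is no figure of the plan's own to reproduce here. The sample-size calculation plays no part. The check is to set the passages side by side, with one calculation to show scale.

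**1. Could a UADE enquiry fill the AE tables?** No, for three reasons.
- Protocol 6.3 limits a UADE to a serious, previously unidentified problem associated with the device. An event before first device use cannot qualify.
- Protocol 6.2.2 lists constipation, diarrhea, nausea, headache and others as anticipated. When not serious, these are AEs and not UADEs.
- SAP 9.1 takes UADEs and SAEs out of the individual-AE summaries. What remains is exactly what the schedule does not list.

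**2. Do other instructions close the gap?** Only in part.
- Protocol 6.1 requires a medical assessment at each scheduled visit, but describes it as the basis for finding UADEs. It names AEs in the extra questioning prompted by an unscheduled healthcare visit or a new medication.
- Concomitant medications appear in the text for Visit 1 and Visits 3 to 5. They do not appear in the Visit 2 text, and Table 1 has no row for them. Visit 2 closes the pre-device window.
- Protocol 4.5 asks for UADE information from subjects who drop out and does not mention AEs.

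**3. When does AE collection start?** No passage says. Under the first sentence of 6.2, a new illness on Day -10 is an AE. Under the third, a condition that worsens on Day -10 has not worsened since device use. Two sites could both follow 6.2 and record different things for Day -14 to Day 0.

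**4. Window lengths.** Protocol 4.2 gives 7 + 7 = 14 days before the device and 90 days on it; 90/14 = 6.4. SAP 9.1 counts each subject once per level and plans no adjustment for exposure.

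**5. Scale, under assumptions.** Assume a constant rate of r AEs per subject per 90 days, no device effect, and a fraction q of pre-device events captured. All on-device events are taken as captured. Then:
- Standard of Care column: 1 − exp(−r × (14/90) × q)
- RELiZORB column: 1 − exp(−r)

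| r (assumed) | Standard of Care, q = 1 | Standard of Care, q = 0.5 | RELiZORB |
|---|---|---|---|
| 0.5 | 7.5% | 3.8% | 39.3% |
| 1 | 14.4% | 7.5% | 63.2% |
| 3 | 37.3% | 20.8% | 95.0% |

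The two columns differ widely even with full capture, purely because of their length. Incomplete pre-device capture widens the gap. Incomplete capture on the device works the other way: at r = 1, if only half of on-device events were captured, the RELiZORB column would read 1 − exp(−0.5) = 39.3% instead of 63.2%. The values of r and q are illustrative; none comes from the documents.

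**The case against.** The strongest reply is that the protocol does require AE collection. The synopsis and 7.7 say AEs are recorded. Section 4.8.1 includes AEs in continual safety monitoring, 6.2.1 has the investigator judge causality for each reported AE, and 6.1 makes all staff responsible for complete safety data and expects both volunteered and elicited complaints. Section 6.1 may also use UADE loosely for any complaint. The eCRF, which the SAP's authors reviewed, may prompt for AEs at every visit, and the SAP lists AEs for all enrolled subjects, not only exposed ones. Most anticipated events are gastrointestinal, and the symptom diary solicits such symptoms daily before the device and again before Days 30, 60 and 90.

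Much of this stands. A reader might infer that AEs go uncollected, or that 6.2 simply excludes pre-device events. The documents support neither: they conflict, and the first sentence of 6.2 is broad enough to cover those events. Nor does the SAP test one column against the other; section 9 makes the safety summaries descriptive.

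The reply does not remove the conflict. A general statement in the statistical section is not a visit instruction, and the eCRF is not among the documents. The diary is summarised separately from AEs and covers 3 × 7 = 21 of the 90 treatment days. The symptoms named in the diary-related endpoint (protocol 3.2) omit constipation, diarrhea, nausea, heartburn, indigestion and headache, all of which 6.2.2 lists.

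**Conclusion.** The point holds as a conflict between passages that must be reconciled. The analysis needs non-serious AEs from before and after first device use. The schedule and visit text, followed as written, do not tell sites to ask for them, and nothing fixes when collection starts. AE counts may therefore be incomplete and uneven between sites, with the pre-device column most exposed.

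No size or net direction can be given. Under-capture before the device would make RELiZORB look worse by comparison; under-capture during treatment would make it look better. A reader might infer that the plan flatters the device, or is stacked against it, but the documents show neither.

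The absence of an AE row in Table 1 is clear. The visit columns in which the UADE row is marked cannot be read reliably from the text of the table, so nothing here rests on them. The conclusion assumes that sites work mainly from Table 1 and protocol 4.3. An eCRF that asks about AEs at every visit from consent would reduce the practical effect, though the documents would still need to agree.

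**What to change.** - **Table 1, protocol and SAP:** make the row 'Adverse events and UADEs', running from consent at Visit 1 through Visit 5.
- **Protocol 4.3, Visits 3 to 5:** write 'assess AEs and UADEs' in both places.
- **Protocol 4.3, Visit 2:** add an AE enquiry covering Day -14 to Day 0.
- **Protocol 6.2:** replace the device-use wording with 'since informed consent'. The start-date rule in SAP 9.1 can then sort events into columns without change.
- **If the change comes too late for some subjects:** keep the Standard of Care column and add a footnote that pre-device AEs were not systematically solicited and that the windows differ (about 14 versus 90 days). Dropping the column would discard recorded safety data.

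The cost is an amendment to wording and one standard question at visits that already take place. The downside is more non-serious AEs to enter and a higher reported AE count.
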